7.11.2.4 Patients Reaching a Specific Reduction in *S. aureus* Carriage

For each patient, the log₁₀ CFU/mL *S. aureus* values obtained prior to third dose, immediately prior to surgery, within 1 hour of incision closure, 48 hours after surgery and 6 days after surgery will each be subtracted from their baseline log₁₀ CFU/mL *S.*

aureus value to determine the reduction in their log₁₀ CFU/mL S. aureus nasal carriage.

A plot of the proportion of patients with a range of specific reductions in log₁₀ CFU/mL *S. aureus* nasal carriage from baseline will be presented for each treatment group for each time point of interest. Cut-offs in intervals of 0.5 log₁₀ CFU/mL will be considered in the first instance, but other intervals will be considered as appropriate. The plot will present the percentage of patients with a reduction greater than or equal to the cut-off. Treatment groups will be represented by different symbols and line style. The reductions at the time-points of interest will be presented on separate plots. A supporting table containing the proportion of patients with a range of specific reductions in log₁₀ CFU/mL *S. aureus* nasal carriage presented by treatment group and time point will also be produced.

7.11.2.5 Proportion of patients with nasal carriage below a specific cut-off

The proportion of patients with a nasal carriage of log₁₀ CFU/mL *S. aureus* considered in intervals of 0.5 will be presented using methods described in section 6.11.2.4, presenting the percentage of patients below the cut-off. Alternative intervals will be used as appropriate.

7.11.2.6 Nasal carriage according to semi-quantitative categorization

A semi-quantitative categorization will be used to categorize *S. aureus*. nasal carriage. The categories are:

S. aureus nasal carriage (CFU/mL)	Semi-Quantitative Scale Category
0	Negative
1-10	0
>10-100	1
>100-1,000	2
>1,000-10,000	3
>10,000-100,000	4
> 100,000	5

The category for each *S. aureus* nasal carriage value at all time points will be listed.

7.11.2.7 Proportion of patients with a 2-log drop in *S. aureus*

A 2-log drop in log₁₀ CFU/mL *S. aureus* is defined as a value which is 100 times smaller than their baseline *S. aureus* value. The 2-log drop in *S. aureus* will be determined from the values obtained from prior to the third dose through to 6 days after surgery.

The percentage of patients with a 2-log drop in log₁₀ CFU/mL *S. aureus* will be summarized.

A flag will be added to the listing of *S. aureus* data to indicate patients identified as having a 2-log drop in *S. aureus* nasal carriage.

7.11.2.8 Difference in *S. aureus* Post-operative Infections

The number of patients experiencing post-operative infections will be calculated from study treatment to 30 days after surgery (or 90 days after surgery in the case of an object implant). Post-operative infections (as recorded on the 'Post-Operative

Infection' CRF page) include, but are not limited to, surgical site infection, bloodstream infections, catheter-related infections and implant infections. Descriptive statistics for the number of post-surgery days per patient will also be presented. For patients who have not reached 30 days after surgery at the time of analysis (or 90 days after surgery in the case of an object implant), the number of post-surgery days per patient will be calculated as (date of early study withdrawal – date of surgery) + 1. The number and percentage of subjects not reaching 30 days (or 90 days in the case of an object implant) will also be presented.

The number and percentage of patients with post-operative infections will be presented for each treatment group together with the severity of these infections and the bacterial strains identified.

All post-operative infection data will be listed.

7.11.3 Exploratory Endpoints

7.11.3.1 Post-operative Antibiotic Use

The reason for post-operative prescribed anti-staphylococcal antibiotic use during the 30-day post-operative period (90 days in the case of an object implant) will be summarized by treatment group.

The reason for the post-operative antibiotic use will be obtained from the indication field of the concomitant medication page of the CRF. A medical review will be performed on an ongoing basis to ensure that indication field in the CRF is correct. The number and percentage of patients within each category will be presented in a summary table and categories assigned will be included in the medication listing. Duration of post-operative staphylococcal antibiotics will also be summarized. Where a patient took more than one post-operative staphylococcal antibiotic medication, the total duration of all post-operative staphylococcal medications taken by the patient will be summarized.

7.11.3.2 Change in S. aureus log CFU/mL following surgery

The change in *S. aureus* log₁₀ CFU/mL from within 1 hour of incision closure will be described graphically to identify any rebound effects.

A plot of the mean *S. aureus* log₁₀ CFU/mL with error bars will be presented over time for each treatment group. The plot will display both treatment groups on the same graph. Each pre-surgery and post-surgery time point (baseline, prior to the third dose of study drug, immediately prior to surgery, within 1 hour of incision closure, 48 hours after surgery and 6 days after surgery) will be included to provide a complete depiction of the *S.* aureus log₁₀ CFU/mL values over time.

Additionally, a plot of the individual patient data for S. aureus log₁₀ CFU/mL will be presented over time. A separate plot will be produced for each treatment group with each patient represented by a separate line on the same plot. Each pre-surgery and post-surgery time point (baseline, prior to third dose, immediately prior to surgery, within 1 hour of incision closure, 48 hours after surgery and 6 days after surgery) will be included.

7.12 Multiplicity

All secondary endpoints will be considered as descriptive evidence of efficacy and will be analyzed without any procedures to account for multiple comparisons.

7.13 SAFETY EVALUATION

The safety and tolerability of 0.2% w/w XF-73 will be assessed based on adverse events, nasal examinations, brief smell identification test and safety evaluations including clinical laboratory evaluations and vital signs.

7.13.1 Adverse Events

Adverse events (AEs) will be coded using the MedDRA dictionary version 23.1. The version used will be indicated in the data summaries and listings.

AEs will be collected between screening and 6 days after surgery.

An AE occurring after written screening consent has been obtained but before the first dose of study drug, the AE will be considered a non-treatment emergent AE. These events will be reported in the medical history summaries.

A TEAE is defined as an AE that occurs from the time the patient receives their first dose of the study drug until the patient's Day 6 visit, or for serious AEs (SAEs) considered related to study drug, until the final follow-up visit. Note only AEs meeting the serious SAE criteria and considered related to study drug will be recorded between the Day 6 visit and the final follow up visit (Day 30 or Day 90 in the case of an object implant).

If a subject discontinues treatment but has an AE occurring from the time of first dose and on or prior to Day 6 (Date of first dose (Day 0) + 6 days) then this will be considered a TEAE. Any AE occurring after Day 6 for a discontinued subject will not be considered treatment-emergent unless it meets the SAE criteria.

If adverse event dates are incomplete and it is not clear whether the adverse event was treatment-emergent, it will be assumed to be treatment-emergent. If the TEAE has a missing relationship it is assumed to be related to the study drug for analysis purposes.

A summary table will present the following:

- TEAEs (number of events and number of patients).
- Serious TEAEs (number of events and number of patients).
- Serious study drug-related TEAEs (number of events and number of patients).
- TEAEs by severity (mild/moderate/severe) (number of events and number of patients).
- TEAEs by relationship to study drug category (Not related/Related) (number of events and number of patients).
- TEAEs leading to withdrawal of study drug (number of patients only).
- Study drug-related TEAEs leading to withdrawal of study drug (number of patients only).
- TEAEs leading to death (number of patients only).

In the above summaries, if a patient experienced more than one TEAE, the patient will be counted once using the most related event for the "by relationship to study drug" and "study drug-related" summaries and at the worst severity for the "by severity" summary.

The following tables will be presented for events and patients:

- 1. TEAEs by System Organ Class (SOC) and Preferred Term (PT).
- 2. TEAEs by SOC and PT –ENT flagged events (as indicated on the 'Adverse Events' CRF page).
- 3. TEAEs by PT.
- 4. TEAEs by SOC, PT and severity.
- 5. TEAEs by SOC, PT and relationship to study drug.

For all of the above, SOC and PT will be presented in decreasing frequency of the total number of patients in the 0.2% XF-73 nasal gel treatment group with TEAEs.

Further details of the above five tables are given below:

- 1. If a patient experienced more than one TEAE, the patient will be counted once for each SOC and once for each PT.
- 2. If a patient experienced more than one ENT TEAE, the patient will be counted once for each SOC and once for each PT.
- 3. If a patient experienced more than one TEAE, the patient will be counted once for each PT.
- 4. If a patient experienced more than one TEAE, the patient will be counted once for each SOC and once for each PT at the worst severity.
- 5. If a patient experienced more than one TEAE, the patient will be counted once for each SOC and once for each PT using the most related event.

Adverse event data will be listed in full and this will also include a treatment emergent flag, an ENT finding flag, the time of onset and cessation of event relative to first dosing of study drug and duration of AE.

7.13.2 Clinical Laboratory Evaluation

Observed values and change from baseline in hematology, biochemistry and urinalysis assessments will be summarized over time. If the test results are reported in categorical format, the results will be summarized by patient counts and percentage for each category.

Each hematology and biochemistry parameter will be classed as low, normal, high or missing based on the reference ranges. Shift tables in relation to the normal range from baseline over time will be presented.

Hematology, biochemistry and urinalysis data will be listed separately including change from baseline, reference ranges flagging all out of range values and their clinical significance.

Scatterplots of key hematology parameters (Hemoglobin, White blood cell count, Neutrophils count, Lymphocyte count and Platelets) and key biochemistry parameters (Creatinine, Alanine aminotransferase, Aspartate aminotransferase, Total bilirubin and Alkaline phosphatase) will be produced, with measured value appearing on the y-axis and time (days since first administration of study drug) on the x-axis. The relevant reference range will be overlaid on the plot as a reference line. Parameters will be presented in the same order as the CRF.

Listings of clinically significant hematology, biochemistry and urinalysis laboratory measurements recorded throughout the study will be provided.

7.13.3 Vital Signs

Vital sign observed values and change from baseline by parameter will be summarized over time.

Parameters will be presented in the same order as the CRF.

All vital sign data will be listed including change from baseline and flags for substantial changes from baseline and reference ranges flagging all out of range values.

7.13.4 Physical Examination

Details of timings of physical examinations will be listed.

7.13.5 Pregnancy Test

Pregnancy test details will be listed.

7.13.6 Nasal Examination

Nasal examinations will be carried out by an ear nose and throat (ENT) specialist at Baseline and 48 hours after surgery.

The number of patients with a clinically significant nasal examination will be summarized at each time point by treatment group.

All data from the nasal examinations will be listed.

7.13.7 Brief Smell Identification Test[™] (B-SIT)

The Brief Smell Identification Test (B-SIT) is a measure of olfactory function which is self-administered in a 'scratch and sniff' format. An accompanying questionnaire has 4 possible options for each of the 12 odorants tested. If the patient does not perceive an odor a response must still be entered.

A patient scores 1 point for every correctly identified scent and the overall score is derived as the total correct scents identified out of 12, with higher scores indicating a better olfactory performance.

The percentile rank of the score is determined using the B-SIT interpretation matrix which is divided into age groups and differs between the sexes. This percentile rank is then used by the investigator to attribute the patient to one of the following three categories: abnormal relative to age, deficit relative to younger persons and normal. The data will be presented as collected on the CRF. If the score is so low that the percentile rank is not quantifiable the percentile and the category will both be entered as 'below percentile rank'.

B-SIT data will be summarized using shift tables, in relation to the normal category, from baseline over time.

A medical review will be performed on an ongoing basis in the CRF to identify medical history and adverse events linked to subjective impact on smell. The baseline B-SIT score will be compared to any smell related medical history events (those with 'Was this medical history an ENT finding?' = Yes) and the Day 6 B-SIT score will be compared to any smell related TEAEs (those with 'Was this event an ENT finding?' = Yes).

All B-SIT data will be listed including change from baseline for the B-SIT score.

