4.3 Risk-Benefit Assessment

The safety of nasal application of XF-73 in concentrations up to 2 mg/g, cumulative doses up to 13.2 mg and for up to 5 days has already been studied in 172 volunteers. The most common AEs reported as related to XF-73 have been nasal discomfort, headache and rhinorrhoea in 17, 14 and

14 patients, respectively. These events were mostly mild in intensity, transient and resolved spontaneously without sequelae. Post-dose nasal examinations have not revealed erythema or increased secretions, so these events seem to be more related with the physical presence and sensation of the gel in the nares rather than a physiological interaction with the nasal mucosa; though a dose response cannot be fully ruled out.

Only one suspected unexpected serious adverse reaction (SUSAR), hyposmia, has been reported; and has also been the only related serious adverse event so far. This was in study DMID11-007 and since this report the remaining 21 volunteers were provided a smell test pre- and post- study. No signal was detected.

XF-73 plasma levels have been determined in all studies up to date showing no evidence of systemic absorption (assay detection limit 0.2 ng/mL), therefore no systemic toxicity from XF-73 is expected in this study. Of note, in the studies with XF-73 nasal gel to date, there have been no AEs leading to treatment or study discontinuation.

XF-73 provided as a nasal gel has been shown to be well tolerated in different healthy volunteer studies; nevertheless in this Phase 2 study, with patients who will undergo surgery, besides the usual safety exams (physical, biochemistry and haematological laboratory tests) a nasal examination by an ear nose and throat (ENT) specialist will be performed pre and post-dosing to further assess the risks from the contact of XF-73 gel and the nasal mucosa as well as a pre-post-dosing smell test to address the possible risk of hyposmia as it was seen in study DMID11-007.

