2.2 Study Endpoints

The primary endpoint of the study is the change in *S. aureus* log CFU/mL from baseline to pre-surgery.

The secondary endpoints are:

- Difference in AUC of S. aureus log CFU/mL from baseline to pre-surgery.
- Difference in AUC of S. aureus log CFU/mL from baseline to immediately post-surgery.
- Change in S. aureus log CFU/mL from baseline to immediately after surgery.
- Change in S. aureus log CFU/mL from baseline to 48 hours after surgery.
- Change in S. aureus log CFU/mL from baseline to 7 days after surgery.
- Percentage of patients reaching a specific reduction in S. aureus carriage prior to surgery, immediately post-surgery and on Day 6 ± 24hrs.
- Difference in the incidence of *S. aureus* post-operative infections during the 30-day period after surgery (90 days in the case of foreign implant).
- Incidence of Treatment Emergent Adverse Events (TEAEs) from the first dose of study medication to 7 days post last application of study medication.
- Changes in vital signs, safety clinical laboratory assessments, nasal examination and smell identification test.

The exploratory endpoint is the reason for post-operative prescribed anti-staphylococcal antibiotic use during the 30-day post-operative period (90 days in the case of an object implant).

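### The B-SIT smell test is summarised by arm only as category shifts; the 0–12 score change is derived but only listed, so small average losses can be missed

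*SAP*

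**What the plan says.** Protocol 4.3 gives the reason for the test. "Only one suspected unexpected serious adverse reaction (SUSAR), hyposmia, has been reported", and it "has also been the only related serious adverse event so far". The same section therefore adds a pre- and post-"dosing smell test to address the possible risk of hyposmia as it was seen in study DMID11-007". It also reports that the 21 volunteers still to be tested in that study had smell tests before and after, with no signal.

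SAP 2.2 includes the test in a secondary safety endpoint: "Changes in vital signs, safety clinical laboratory assessments, nasal examination and smell identification test".

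SAP 7.13.7 sets out the data and their use:

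- Score: "the overall score is derived as the total correct scents identified out of 12", with higher scores better.
- Category: the investigator uses an age- and sex-specific percentile rank to assign "one of the following three categories: abnormal relative to age, deficit relative to younger persons and normal". A score too low to rank is entered as 'below percentile rank'.
- Summary: "B-SIT data will be summarized using shift tables, in relation to the normal category, from baseline over time".
- Listing: "All B-SIT data will be listed including change from baseline for the B-SIT score".
- Review: Day 6 scores are compared with smell-related treatment-emergent adverse events.

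Protocol 9.3.6.2 adds that a significant worsening of the olfactory diagnosis at Day 6 is recorded as an adverse event. Protocol 10.1.2, 10.1.3.1 and 10.1.4.2 place the test once before dosing and once at Day 6, so there is one change per patient.

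**The concern.** The endpoint is change in the smell test, and the change in score is already computed. The only by-arm view of it is a table of movements between categories. A patient whose score falls without crossing a category boundary counts there as unchanged.

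The plan treats other safety measures more fully. SAP 7.13.2 and 7.13.3 give laboratory values and vital signs by-arm summaries of observed values and change from baseline, and haematology and biochemistry get shift tables as well. The smell score, which has a specific earlier event behind it, gets only the shift table. SAP 7.14 does not comment on this.

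Protocol 4.3 counts the smell test among the surveillance measures behind its favourable risk-benefit conclusion. If the average score fell modestly on XF-73, the shift table could look much the same in both arms.

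**Working it through.** **The plan's own figures.** The documents give no B-SIT precision, SD, cut-off or baseline distribution. Their only power statement concerns the primary endpoint (protocol 11.10, SAP 3), and it reproduces. With 40 per arm, a difference of 1.5 and SD 2, the SE is 2 × √(2/40) = 0.447, and 1.5/0.447 − 1.96 = 1.39, giving 91.8% (91.2% with the t distribution) against the stated 90%. It says nothing about the smell test.

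**Which losses leave the category unchanged.** Suppose the lowest normal score is 8 or 9 (assumed). A patient stays in normal when the score after the loss is still at or above that value.

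| Lowest normal score | Loss | Baseline scores that cross | Baseline scores that stay normal |
|---|---|---|---|
| 8 | 1 | 8 | 9–12 |
| 8 | 2 | 8, 9 | 10–12 |
| 8 | 3 | 8–10 | 11, 12 |
| 9 | 1 | 9 | 10–12 |
| 9 | 2 | 9, 10 | 11, 12 |
| 9 | 3 | 9–11 | 12 |

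**How much this matters by arm.** This was simulated on assumed inputs:

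- 60 patients per arm (125 randomised 1:1 gives about 62, less a few without both tests).
- True baseline score normal, mean 10 or 10.5, SD 1.2; test error SD 0.8 at each visit. A noisier setting has mean 10 and SDs 1.5 and 1.2.
- Observed scores rounded to integers and held within 0–12. The resulting SD of change is about 1.1 to 1.6.
- Loss subtracted from the XF-73 arm only; 4,000 trials per setting.
- Score: t-test on change. Shift: Fisher exact test on moving from normal to not normal. Both at two-sided 5%.

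The tests only measure how much information each summary carries; protocol 11.8 plans no formal safety comparisons.

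| Baseline mean, lowest normal score | 1-point loss: score | 1-point loss: shift | 2-point loss: shift |
|---|---|---|---|
| 10, 8 | 99.4% | 34.8% | 99.6% |
| 10, 9 | 99.3% | 65.8% | 99.9% |
| 10.5, 8 | 99.3% | 13.7% | 97.1% |
| 10.5, 9 | 99.5% | 54.7% | 100% |
| 10 (noisier), 8 | 86.7% | 30.1% | 94.9% |
| 10 (noisier), 9 | 87.2% | 39.4% | 96.6% |

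For a 2-point loss the score detects about 100% in every setting.

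*Loss in a quarter of XF-73 patients* (mean 10, less noisy setting):

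- 3 points: score 79%; shift 69% (lowest normal 8) or 59% (lowest normal 9).
- 4 points: score 91%; shift 91% or 72%.

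*Share of patients normal at baseline who still read normal* is 1 − (proportion crossing ÷ proportion normal at baseline). For mean 10.5, lowest normal 8 and a 1-point loss, 1 − 0.071/0.98 = 93%. Across all settings it is 70–93% for 1 point, 42–77% for 2 points and 17–51% for 3 points.

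**Precision of the missing summary.** The 95% CI half-width for the difference in mean change is 1.96 × SD × √(2/60): 0.39 point at SD 1.1 and 0.57 at SD 1.6. On these assumptions a descriptive table would locate the average change to about half a point.

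**The case against.** A reader might infer that the shift table hides most of a moderate loss of smell. The documents do not support that. They define no moderate loss and give no cut-offs or SD. On the assumptions above, 'most' is right for 1 point, depends on the cut-off for 2 points, and is generally wrong for 3. A uniform 2-point loss would still separate the arms in the shift table 95–100% of the time.

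A reader might also infer that hyposmia is the only safety concern and otherwise goes unwatched. Protocol 4.3 also names nasal discomfort, headache, rhinorrhoea and contact of the gel with the mucosa, and reports no signal in the volunteers tested afterwards. Individual losses have other routes: the adverse event rule, the table of ENT-flagged events (SAP 7.13.1), the comparison with smell-related events, the listings and the IDMC.

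Further points have force. Safety is descriptive, so power is only a measure of information. A single cut-off is cruder than the planned table, whose age- and sex-specific categories may keep more information. The concern arose from one individual, and one patient in 60 losing 6 points moves the arm mean by only 0.1 (6/60), whereas a shift or adverse event shows that patient directly. The table shells are a separate document that was not available, and protocol 11.8 promises descriptive summaries of all safety data, so a score table may exist there.

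What does not stand is that these routes replace the missing summary. The adverse event rule depends on the same olfactory diagnosis, and 'significantly' is undefined. The comparison with events covers only patients who have one. Listings do not give a contrast between arms.

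**Conclusion.** The point holds in limited form. SAP 7.13.7 specifies no by-arm summary of a score change it already derives, for a test introduced to address a named risk. The shift table can miss small average losses and is less informative about losses confined to a subset; larger losses would mostly still be visible.

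For a uniform 1-point loss the illustrative contrast is 87–99% from the score against 14–66% from the shift; at 2 points the two nearly converge. The direction was the same throughout, with the shift never ahead beyond simulation error. The sizes rest wholly on the assumed baseline, noise, cut-offs and 60 patients per arm. This is a reporting weakness in a descriptive safety analysis, worth correcting because correction is cheap. The primary analysis is unaffected.

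**What to change.** In SAP 7.13.7, add one table by treatment group on the safety set:

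- B-SIT score at baseline and Day 6, and change from baseline to Day 6: n, mean, SD, median and range.
- Difference between arms in mean change with a 95% CI, labelled as description only.
- Numbers and percentages losing at least 2, 3 and 4 points. These should be read against placebo, because some 2-point drops are test noise. With a change SD of 1.2 and no true loss, a rounded change of −2 or worse has probability Φ(−1.5/1.2) = Φ(−1.25), about 11%.

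Keep the shift table, and state where 'below percentile rank' falls in it. If the table shells already contain a score summary, the SAP text should say so.

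The cost is one extra table from a variable already derived for the listing, with no new data.
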